6.3.1.4 Alpelisib

For patients who do not tolerate the protocol-specified dosing schedule, dose adjustments are permitted in order to allow the patient to continue the study treatment. All dose modifications must be based on the worst preceding toxicity as graded by the NCI Common Terminology Criteria [NCI-CTCAE v4.03]. If the administration of alpelisib is interrupted for reasons other than toxicity, then treatment with alpelisib may be resumed at the same dose.

A maximum of 2 dose reductions of alpelisib from the recommended starting dose may be allowed before considering discontinuation of alpelisib treatment.

Please refer to Table 6-2 and Table 6-3 for guidance.

Table 6-2 Dose reduction sequential steps for alpelisib

Alpelisib dose level	Dose and schedule	Number of tablets & strength
Starting dose	300 mg/day continuously	1 x 200 mg tablet and 2 x 50 mg tablet
Dose level -1	250 mg/day continuously	1 x 200 mg tablet and 1 x 50 mg tablet
Dose level -2	200 mg/day continuously	1 x 200 mg tablet

Recommendations for dose reduction or dose interruption of alpelisib in the management of adverse reactions are summarized in Table 6-3. Adverse events for alpelisib are graded according to (Common Terminology Criteria for Adverse Events (CTCAE) v4.03 since this version is more objective with regards to hyperglycemia grading since it is based on laboratory values. Clinical judgment of the treating physician, including confirmation of lab values if deemed necessary, should guide the management plan of each patient based on individual benefit/risk assessment.

However, treatment must be discontinued as indicated in Table 6-3.

After treatment is resumed at a lower dose:

- If the same toxicity recurs with the same severity, then the next treatment re-initiation must resume at a lower dose irrespective of duration.
- Once the alpelisib dose has been reduced, no re-escalation will occur, even upon resolution of AE.

If a participant requires a withholding of alpelisib dose, the participant should continue combination drug, per investigator discretion. All scheduled assessments will continue to be performed as per protocol.

If administration of alpelisib dosing is held for more than 28 days, then alpelisib must be permanently discontinued. Grade 4 adverse events will lead to permanent discontinuation, irrespective of recovery time, unless otherwise specified. Patients requiring more than 2 dose reductions for alpelisib should be permanently discontinued.

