	 If resolved in ≤ 7 days, then maintain dose level If resolved in > 7 days, then ↓ 1 dose level
Grade 3 (> 3.0 – 6.0 x ULN)	Permanently discontinue patient from alpelisib
Grade 4 (> 6.0 x ULN)	Permanently discontinue patient from alpelisib
Investigations (Hepatic)	
Isolated total Bilirubin elevation	
Grade 1 (> ULN - 1.5 x ULN)	No dose adjustment is required. Initiate appropriate medical therapy and monitor as clinically indicated.
Grade 2 (> 1.5 - 3.0 x ULN)	 Interrupt dose until recovery to Grade ≤ 1 and resume at the same dose if resolved in ≤ 14 days or resume at the next lower dose level if resolved in > 14 days.
Grade 3 (> 3.0 - 10.0 x ULN)	Interrupt dose until recovery to Grade ≤ 1, then resume at the next lower dose level.
Grade 4 (> 10.0 x ULN)	Permanently discontinue.
Isolated AST or ALT Elevation	
Grade 1 (> ULN – 3.0 x ULN)	No dose adjustment is required. Initiate appropriate
Grade 2 (> 3.0 - 5.0 x ULN)	medical therapy and monitor as clinically indicated.
Grade 3 (> 5.0 - 10.0 x ULN)	 Interrupt dose until recovery to Grade ≤ 1, then resume at the next lower dose level.
Grade 4 (> 10.0 x ULN)	Permanently discontinue
Combined elevations of AST or ALT and total Bilirubin	Please see specific instructions in Section 6.3.2.2
Investigations (Gastrointestinal)	
Diarrhea is defined as: A disorder characterized by freq	uent and watery bowel movements.
Colitis is defined as a disorder characterized by inflamm	nation of the colon. (see also Appendix 2)
Grade 1 (Increase of < 4 stools per day over baseline; mild increase in ostomy output compared to baseline) OR	Maintain dose level but initiate appropriate medical therapy and monitor as clinically indicated
Asymptomatic colitis; clinical or diagnostic observations only; intervention not indicated	
Grade 2 (Increase of 4 - 6 stools per day over baseline; moderate increase in ostomy output compared to baseline)	Omit dose until resolved to ≤ Grade 1, initiate appropriate medical therapy then restart at same dose.
limiting instrumental Activities of Daily Living (ADL)	If diarrhea returns as ≥ Grade 2, then omit dose until resolved ≤grade1, then decrease 1 dose level
OR	
Abdominal pain; mucus or blood in stool	Initiate or intensify appropriate medical therapy and monitor as clinically indicated.
	For Grade 2 colitis consider additional treatment, such as steroids.

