14.4 Appendix 4 – Liver event and Laboratory trigger Definitions and Follow-up Requirements

Table 14-5 Liver event and laboratory trigger definitions

	Definition/ threshold
Liver laboratory triggers If ALT, AST and total bilirubin normal at baseline:	· ALT or AST > 5 × ULN · ALP > 2 × ULN (in the absence of known bone pathology) · Total bilirubin > 3 × ULN (in the absence of known Gilbert syndrome) · ALT or AST > 3 × ULN and INR > 1.5 · Potential Hy's Law cases (defined as ALT or AST > 3 × ULN and Total bilirubin > 2 × ULN [mainly conjugated fraction] without notable increase in ALP to > 2 × ULN) · Any clinical event of jaundice (or equivalent term) · ALT or AST > 3 × ULN accompanied by (general) malaise, fatigue, abdominal pain, nausea, or vomiting, or rash with eosinophilia · Any adverse event potentially indicative of a liver toxicity*
If ALT or AST abnormal at baseline:	· ALT or AST > 2x baseline or > 300 U/L (whichever occurs first)

^{*}These events cover the following: hepatic failure, fibrosis and cirrhosis, and other liver damage-related conditions; non-infectious hepatitis; benign, malignant and unspecified liver neoplasms ULN: upper limit of normal

Table 14-6 Follow-up requirements for liver laboratory triggers with liver symptoms

ALT	TBL	Liver Symptoms	Action
ALT increase without b	ALT increase without bilirubin increase:		
If normal at baseline: ALT > 3 x ULN	Normal For participants with	None	· No change to study treatment
If elevated at baseline: ALT > 2 x baseline	Gilbert's syndrome: No change in baseline TBL		· Measure ALT, AST, ALP, GGT, TBIL, INR, albumin, CK, and GLDH in 48-72 hours.
or > 300 U/L (whichever occurs first)			· Follow- up for symptoms.
If normal at baseline: ALT > 5 x ULN for more than two weeks	Normal For participants with Gilbert's syndrome: No	None	· Interrupt study drug · Measure ALT, AST, ALP, GGT, TBIL, INR,
If elevated at baseline: ALT > 3 x baseline or > 300 U/L (whichever occurs	change in baseline TBL		albumin, CK, and GLDH in 48-72 hours. · Follow- up for symptoms.

ALT	TBL	Liver Symptoms	Action
first) for more than two weeks			Initiate close monitoring and workup
If normal at baseline: ALT > 8 x ULN	Normal	None	for competing etiologies.
ALT increase with bilir	ubin increase:		 Study drug can be restarted only if
If normal at baseline: ALT > 3 x ULN	TBL > 2 x ULN (or INR > 1.5)	None	another etiology is identified and liver

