If elevated at baseline: ALT > 2 x baseline or > 300 U/L (whichever occurs first)	For participants with Gilbert's syndrome: Doubling of direct bilirubin		enzymes return to baseline.
If normal at baseline: ALT > 3 x ULN	Normal or elevated	Severe fatigue, nausea, vomiting, right	
If elevated at baseline: ALT > 2 x baseline or > 300 U/L (whichever occurs first)		upper quadrant pain	

Table 14-7 Follow-up requirements for liver laboratory triggers

Criteria	Actions required	Follow- up monitoring
Total Bilirubin (isolated)		
>1.5 – 3.0 ULN	Maintain treatment Repeat LFTs within 48-72 hours	Monitor LFTs weekly until resolution ^c to ≤ Grade 1 or to baseline
> 3 - 10 × ULN (in the absence of known Gilbert syndrome)	Interrupt treatment Repeat LFT within 48-72 hours Hospitalize if clinically appropriate Establish causality Record the AE and contributing factors (e.g. conmeds, med hx, lab) in the appropriate CRF	Monitor LFTs weekly until resolution ^c to ≤ Grade 1 or to baseline (ALT, AST, total bilirubin, Alb, PT/INR, ALP and GGT) Test for hemolysis (e.g. reticulocytes, haptoglobin, unconjugated [indirect] bilirubin)
> 10 x ULN	Discontinue the study treatment immediately Hospitalize the participant Establish causality Record the AE and contributing factors(e.g. conmeds, med hx, lab) in the appropriate CRF	ALT, AST, total bilirubin, Alb, PT/INR, ALP and GGT until resolution ^c (frequency at investigator discretion)

Criteria	Actions required	Follow- up monitoring
Any AE potentially indicative of a liver toxicity*	Consider study treatment interruption or discontinuation Hospitalization if clinically appropriate Establish causality Record the AE and contributing factors (e.g., conmeds, med hx, lab) in the appropriate CRF	Investigator discretion

^aElevated ALT/AST > 3 × ULN and TBL > 2 × ULN but without notable increase in ALP to > 2 × ULN ^b(General) malaise, fatigue, abdominal pain, nausea, or vomiting, or rash with eosinophilia ^cResolution is defined as an outcome of one of the following: (1) return to baseline values, (2) stable values at three subsequent monitoring visits at least 2 weeks apart, (3) remain at elevated level after a maximum of 6 months, (4) liver transplantation, and (5) death.

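### For isolated total bilirubin >1.5 to 3.0 × ULN, Table 6-3 interrupts alpelisib while Table 14-7 maintains treatment, and no sentence says which table governs

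*Protocol*

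**What the plan says.** Table 6-3, in the Grade 2 row for isolated total bilirubin (above 1.5 to 3.0 × ULN), reads "Interrupt dose until recovery to Grade ≤ 1 and resume at the same dose if resolved in ≤ 14 days". If recovery takes more than 14 days, alpelisib restarts at the next lower level.

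Table 14-7 in Appendix 4 has a row for isolated total bilirubin over the same range. Its required-action column reads "Maintain treatment Repeat LFTs within 48-72 hours", followed by weekly liver tests.

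Section 6.3.1.4 describes the status of Table 6-3: "Recommendations for dose reduction or dose interruption of alpelisib in the management of adverse reactions are summarized in Table 6-3". It adds that "Clinical judgment of the treating physician, including confirmation of lab values if deemed necessary, should guide the management plan of each patient", and then: "However, treatment must be discontinued as indicated in Table 6-3". It also fixes two consequences of a hold. A hold of more than 28 days ends alpelisib permanently, and "Once the alpelisib dose has been reduced, no re-escalation will occur, even upon resolution of AE".

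**The concern.** An investigator with a bilirubin of, say, 2.5 × ULN finds an instruction to stop alpelisib in the body of the protocol and an instruction to keep giving it in the appendix. Both are current text. Acting on either means departing from the other, and Section 12 allows no authorized deviations. At stake are an individual patient's dose, possibly the patient's continuation on alpelisib, and uniform handling of a hepatic signal across sites.

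**Working it through.** No plan figure needs reproducing. The check compares the two tables, looks for a precedence rule, and traces the dosing consequence.

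**Step 1: the two tables, range by range (isolated total bilirubin).**

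| Range (× ULN) | Table 6-3 | Table 14-7 | Same action? |
|---|---|---|---|
| >1.5 to 3.0 | Interrupt until Grade ≤ 1 | Maintain; repeat tests in 48–72 hours | No |
| >3 to 10 | Interrupt | Interrupt (row limited to patients without known Gilbert syndrome) | Yes |
| >10 | Discontinue permanently | Discontinue immediately | Yes |

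Could the treatment that Table 14-7 maintains be only the endocrine partner? The same column interrupts treatment in the next row and discontinues study treatment in the one after, and Section 6.1 defines study treatment to include alpelisib. So the row means that alpelisib continues. Nor does it hand over to Table 6-3 once the repeat test confirms the value; it goes straight to weekly monitoring.

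**Step 2: is there a rule that ranks the tables?**

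- Section 6.1.4 refers continuation of treatment to Section 6.3. It does not mention Appendix 4.
- Section 6.3.1 says interruptions may be recommended or mandated and bars deviation from mandatory ones. It cites Table 6-2, which lists only dose levels.
- Section 6.3.1.4 points to Table 6-3 for interruptions, as recommendations. It contains several obligations: modifications follow the worst preceding toxicity, a recurrence of the same severity restarts lower, long holds end treatment, and discontinuations in Table 6-3 are binding. None of them ranks Table 6-3 above Table 14-7.
- Section 6.3.2.2 covers combined transaminase and bilirubin rises, not isolated bilirubin.
- Table 14-5, for normal baseline liver tests, sets the isolated-bilirubin trigger at "Total bilirubin > 3 × ULN (in the absence of known Gilbert syndrome"). That would put the 1.5 to 3.0 range below the trigger, yet Table 14-7 still gives that range its own action row.

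So there are pointers to Table 6-3 but no precedence rule.

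**Step 3: what follows from the choice of table.** Dose levels are from Table 6-2 (300, 250 and 200 mg/day); hold rules are from Table 6-3 and Section 6.3.1.4. For a patient on 300 mg/day:

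| Time to Grade ≤ 1 | Under Table 6-3 | Under Table 14-7 |
|---|---|---|
| ≤ 14 days | Held, then 300 mg | 300 mg throughout |
| 15 to 28 days | Held, then 250 mg, no re-escalation | 300 mg throughout |
| > 28 days | Alpelisib permanently discontinued | 300 mg throughout |

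Dose difference in the middle row: (300 − 250) / 300 = 0.167, or 16.7% lower.

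**The case against.** The strongest reply is that the body text already gives dosing to Table 6-3. Its title concerns interrupting and restarting alpelisib, and Sections 6.1.4 and 6.3.1.4 both lead there. Its diarrhea and stomatitis rows refer out to Appendices 2 and 3, but its bilirubin rows do not refer to Appendix 4. Table 14-7 is titled as follow-up for liver triggers, and the row in question lies below the Table 14-5 trigger for a normal baseline. On this view it is a stray line, and most investigators would follow Table 6-3.

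Most of that stands, and it limits the size of the problem. It does not remove it. The stray line sits in a column of required actions, while Table 6-3 offers recommendations subject to clinical judgment. On wording alone, the appendix reads as the more binding of the two.

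A second reply is timing. Enrollment was complete by 14-Dec-2020. If the last patient started treatment near that date, the Core Phase (19 months after last patient first treatment) ended around mid-July 2022, before Amendment 6 of 28-Mar-2023. The present text therefore applies to the Extension Phase, where chemistry is done only as clinically indicated (Section 7.1.4). Table 14-7 was listed as updated in Amendment 5, and earlier versions are not available, so the conflict cannot be shown to have existed when most patients were dosed. This stands, and it is why the practical effect is small.

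A reader might infer a further defect: that Table 6-3 traps patients admitted with raised bilirubin because, unlike Table 14-7, it has no return-to-baseline option. The documents do not support treating this as a contradiction. The Table 14-7 words "Grade 1 or to baseline" are in the monitoring column and say when weekly tests may stop; the Table 6-3 target says when dosing may resume. Table 6-3 also manages adverse reactions, and Section 8.1.1 counts a pre-existing condition as an adverse event only if it worsens, so a stable entry value is not clearly a trigger. Whether to relax a hepatic hold for such patients is a clinical choice for which the documents give neither a threshold nor evidence.

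**Conclusion.** The inconsistency is real and limited to one row in each table. For isolated total bilirubin above 1.5 to 3.0 × ULN the protocol both interrupts and maintains alpelisib, and nothing states which instruction prevails. The consequence for a patient on 300 mg/day ranges from a short hold, through a lasting 16.7% dose reduction, to loss of alpelisib, against uninterrupted dosing.

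The number of patients affected is not given. With 9 patients on treatment at the date reported in Amendment 6 (30-Jan-2022), it can now be only a few. The correction is still worth making, because treatment may run up to 36 months in the Extension Phase and a clinically indicated liver test is when an investigator would open these tables.

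A reader might also infer that inconsistent dosing has affected the 6-month progression-free proportion. The documents do not support that: they give neither the frequency of this laboratory finding nor the action that sites took. The sample size, the 44-of-112 criterion and the primary analysis are untouched. The conclusion rests on a comparison of texts and on reading treatment in Table 14-7 as including alpelisib.

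**What to change.** 1. In the Table 14-7 row for isolated total bilirubin above 1.5 to 3.0 × ULN, replace the instruction to maintain treatment with *Manage alpelisib dosing per Table 6-3*. Keep the repeat liver tests and the weekly monitoring.
2. In Section 6.3.1.4, add one sentence stating that Table 6-3 governs alpelisib dosing where Appendix 4 differs.

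Leave the Table 6-3 bilirubin rows, including the recovery criterion, and the eligibility limits as they are.

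The cost is one phrase and one sentence, with no new data or visits. Under Section 12.1 the change needs a written amendment with the usual approvals, so it could be carried in the next amendment made for any other reason.

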Grade 3 (Increase of ≥7 stools per day over baseline; hospitalization indicated; severe increase in ostomy output compared to baseline; limiting self-care ADL)	Omit dose until resolved to ≤ Grade 1, then ↓ 1 dose level
OR	Manage according to local standard of care medical management, including electrolyte monitoring, administration of antiemetics and antidiarrhoeal

Worst toxisity CTCAE Grade (value)	Doca Madifications for alpaliaib	
Worst toxicity – CTCAE Grade (value)	Dose Modifications for alpelisib medicinal products and / or fluid replacement and	
Severe abdominal pain; peritoneal signs	electrolyte supplements as clinically indicated.	
	For Grade 3 colitis consider additional treatment, such as steroids.	
Grade 4 (Life-threatening consequences; urgent intervention indicated)	Discontinue subject from treatment.	
	Manage according to local standard of care medical management, including electrolyte monitoring, administration of antiemetics and antidiarrhoeal medicinal products and /or fluid replacement and electrolyte supplements, as clinically indicated.	
Investigations (Pancreatic)		
Pancreatitis		
Grade 2 (enzymatic elevation or radiologic findings only)	Omit dose until resolved to Grade ≤ 1, then resume treatment at ↓ 1 dose level. If toxicity recurs, permanently discontinue patient from alpelisib	
Grade 3	 Omit dose until complete resolution of symptoms 	
For patients deriving clinical benefit upon investigator's judgement:	and lipase resolved to Grade ≤ 1, then resume treatment at ↓ 1 dose level. Only 1 dose reduction is allowed.	
	 If recovery to ≤ Grade 1 is greater than 28 days, the patient must be discontinued from the study. 	
For other patients:	 If toxicity reoccurs, permanently discontinue patient from alpelisib 	
	Permanently discontinue patient from alpelisib	
Grade 4	Permanently discontinue patient from alpelisib	
Stomatitis/Oral mucositis (see also Appendix 3)		
Grade 1/Tolerable Grade 2	Maintain dose level	
	Non-alcoholic or salt water mouth wash	
Intolerable Grade 2 or Grade 3	First occurrence: hold until ≤ Grade 1 and ↓ 1 dose level (if stomatitis is readily manageable with optimal management, re-introduction at the same level might be considered at the discretion of the investigator).	
	Second occurrence: hold until ≤ Grade 1 and ↓ 1 dose level.	
Grade 4	Permanently discontinue patient from alpelisib	
Skin and subcutaneous tissue disorders		

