	 If rash resolves to ≤ G1 within 10 days systemic corticosteroid may be discontinued.
	Re-start alpelisib dose once rash /skin toxicity is fading but is no longer active (G1):
	at a reduced dose in case of first occurrence If rash/skin toxicity still active in up to 10% BSA
	after more than 14 days, continue oral

Worst toxicity – CTCAE Grade (value)	Dose Modifications for alpelisib
	corticosteroid for at least 48 hours upon re- challenge with alpelisib; if rash and/or pruritus do not reoccur within 48 hours after re-challenge with alpelisib, systemic corticosteroid may be discontinued
	For patients with symptoms like burning and/or pruritus add a non-sedating anti-histamine such as cetirizine once daily during daytime and a sedating anti-histamine such as diphenhydramine once daily at night. Antihistamine regimen should be continued for a minimum of 28 days after re-challenge with alpelisib.
Grade 4	Permanently discontinue patient from alpelisib
(any % BSA associated with extensive superinfection, with IV antibiotics indicated; life-threatening	Consult a dermatologist, strongly recommend documentation by photography and performing a skin biopsy if clinically indicated
consequences)	Treatment may follow guidelines for Grade 3 above with the exception of rechallenge.
	Additional measures may be taken as per local treatment guidance
Any Grade of Stevens-Johnson-Syndrome/Toxic Epidermal Necrolysis/Drug Reaction with Eosinophilia and Systemic Symptoms (DRESS) or other SJS/TEN/DRESS-like severe skin reactions	 Permanently discontinue patient from alpelisib treatment Consult dermatologist, strongly recommend documentation by photography and performing a skin biopsy if clinically indicated. Follow local treatment guidelines for SJS/TEN/DRESS
*"Active" skin toxicities: If there are no new lesions or ne appearance is changing color from red to pale or light b is not to be considered "active" any longer. Treatment re appearance of skin toxicity may fade slowly, over 10 da	rown, it is likely the skin toxicity has begun to fade and eduction can be considered for these areas. The
Investigations (Pulmonary disorders)	
Pneumonitis	
Please see specific instructions in Section 6.3.2.1.1	
Investigations (Metabolic)	
Asymptomatic amylase and/or lipase elevation (see	also Section 6.3.2.1.4)
Grade 1 (> ULN - 1.5 x ULN)	Maintain dose level
Grade 2 (> 1.5 - 2.0 x ULN)	Maintain dose level
Grade ≥ 3 (> 2.0 x ULN)	Omit dose until resolved to baseline, then

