	If resolved in ≤ 14 days, maintain dose level
	If resolved in > 14 days, then ↓ 1 dose level
	Note:
	In cases of isolated amylase elevations only, dosing may be maintained provided amylase fractionation demonstrates that pancreatic amylase is ≤ Grade 1. Monitor total amylase (and

Worst toxicity – CTCAE Grade (value)	Dose Modifications for alpelisib	
	continue to assess fractionated amylase) as specified in Section 6.3.2.1.4	
Note: Withhold study treatment for acute onset of new or progressive unexplained abdominal symptoms, sa severe pain or vomiting; and perform diagnostic procedures (e.g., abdominal CT scan or ultrasound) to exclude pancreatic pathology.		
Investigations (any other)		
Other adverse events		
Grade 1 or 2	Maintain dose level	
Grade 3	Omit dose until resolved to ≤	
	Grade 1, then ↓ 1 dose level	
Grade 4	Permanently discontinue from alpelisib Omit dose for ≥ Grade 3 vomiting or Grade 3 nausea only if the vomiting or nausea cannot be controlled with optimal antiemetic (as per local practice)	

For additional details on the safety profile of alpelisib, please refer to the alpelisib Investigator Brochure.

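### Table 6-3 can place a symptom-free amylase or lipase rise in two rows whose instructions conflict directly at >1.5 to 2.0 x ULN, and no passage says which row governs

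*Protocol*

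**What the plan says.** Both entries are in Table 6-3 (protocol Section 6.3.1.4).

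- **Pancreatitis, under Investigations (Pancreatic).** The lowest grade listed is "Grade 2 (enzymatic elevation or radiologic findings only", with no ULN threshold and no diagnostic criterion. The action is "Omit dose until resolved to Grade ≤ 1, then resume treatment at ↓ 1 dose level", followed by "If toxicity recurs, permanently discontinue patient from alpelisib".
- **"Asymptomatic amylase and/or lipase elevation", under Investigations (Metabolic).** This row is banded by ULN. At Grade 1 and at "Grade 2 (> 1.5 - 2.0 x ULN" the dose is kept. At Grade 3 or above (over 2.0 x ULN) the dose is held until the value is back to baseline. Then "If resolved in ≤ 14 days, maintain dose level"; if resolution takes longer, the dose drops one level. A note allows dosing to go on for an isolated amylase rise when fractionation shows the pancreatic part at Grade 1 or below.

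Section 6.3.1.4 adds "Once the alpelisib dose has been reduced, no re-escalation will occur, even upon resolution of AE". It allows at most two reductions and requires permanent discontinuation after a hold of more than 28 days. It calls the table recommendations to be guided by clinical judgment, but makes discontinuation compulsory where the table indicates it.

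**The concern.** A raised enzyme with nothing else fits the wording of both rows. The Pancreatitis Grade 3 entry waits for symptoms to resolve completely, so the table places symptoms at Grade 3 and leaves Grade 2 as the symptom-free case. That is also the case the asymptomatic row describes.

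The choice of row matters because a reduction cannot be undone and only two are available. Under one reading a second symptom-free rise ends alpelisib; under the other it need not. Reductions, interruptions and discontinuations, with their reasons, are planned outputs (protocol Sections 10.3 and 10.5.2.6; core-phase SAP Section 2.4.1). Relative dose intensity is calculated against 300 mg/day. If the two readings were both used, those summaries would mix two rules.

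**Working it through.** The plan states no figure to reproduce here. The check sets the two rows side by side for an isolated enzyme rise with no symptoms and no radiologic finding.

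| Enzyme value | Read as Pancreatitis Grade 2 | Read as asymptomatic elevation | Difference |
|---|---|---|---|
| >1.5 to 2.0 x ULN | Hold, restart one level lower, stop if it recurs | Dose unchanged | Direct conflict |
| >2.0 x ULN, resolved in 14 days or less | Hold to Grade 1 or below, restart one level lower, stop if it recurs | Hold to baseline, restart at the same dose | Restart dose, restart threshold, recurrence rule |
| >2.0 x ULN, resolved in more than 14 days | Hold to Grade 1 or below, restart one level lower, stop if it recurs | Hold to baseline, restart one level lower | Restart threshold, recurrence rule |

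Up to 1.5 x ULN the enzyme is at Grade 1, which already meets the first row's restart target, so that band is left out. The amylase-fractionation exception is also left out of the table, because it depends on the pancreatic fraction being low.

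**Dose consequence.** Table 6-2 gives a start of 300 mg/day and a first reduction to 250 mg/day: (300 − 250)/300 = 16.7%.

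- Lipase at 1.8 x ULN without symptoms: 250 mg/day after a hold, or 300 mg/day without one. If it recurs: no alpelisib, or 300 mg/day.
- Lipase at 3 x ULN, back to baseline by day 10: 250 mg/day or 300 mg/day.

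**Does other text separate the rows?**

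- The symptom notes in Table 6-3 and Section 6.3.2.1.4 apply only when abdominal symptoms are present.
- Section 6.3.2.1.4 otherwise covers elevations of Grade 3 or above, so it does not reach the >1.5 to 2.0 x ULN band.
- The fractionation note covers isolated amylase, not lipase.
- Inclusion criterion 14 admits fasting amylase up to 2 x ULN. A patient may therefore enter at 1.8 x ULN, inside the asymptomatic row's Grade 2 band and within the enzyme wording of the pancreatitis row. For this patient a restart target of Grade 1 or below (at most 1.5 x ULN) lies under the baseline value.

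None of these states which row applies.

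**How often it could arise.** Table 7-1 schedules fasting lipase and amylase at screening, at Cycle 3 Day 1, thereafter as clinically indicated, and at end of treatment. Cycle 3 Day 1 is the only fixed on-treatment draw. Table 7-2 (Extension Phase) schedules neither enzyme. The documents give no event rate, so no patient count is estimated.

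**The case against.** The strongest reply is that the rows have different subjects. The first grades an event already diagnosed as pancreatitis; the second names the laboratory finding, gives ULN bands and points to its own follow-up section. A lipase of 1.8 x ULN without symptoms matches the second row's title and band exactly, and a specific rule usually prevails over a general one. The fractionation note treats an isolated amylase rise as a laboratory matter. Section 6.3.2.1.4 treats raised enzymes and pancreatic pathology as separate questions. Inclusion criterion 14 would otherwise admit patients who meet a hold criterion on Day 1, while exclusion criterion 18 bars recent acute or past chronic pancreatitis. The amylase points do not carry over to lipase, which inclusion criterion 15 limits to ULN at entry.

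This reading is plausible and may be what was intended, but it has to be inferred. The pancreatitis row gives no criterion beyond the enzyme or imaging finding. Clinical judgment does not settle it either: Section 6.3.1 forbids departing from mandatory interruptions and reductions, and the stop on recurrence is one of the discontinuations that Section 6.3.1.4 makes binding.

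Two further replies stand. Centers are pooled and no center effect is assessed (core-phase SAP Section 2.1), so no planned analysis compares sites. Enrollment is complete, and the Amendment 6 summary counts 9 patients on treatment as of 30-Jan-2022, so few decisions are left to change.

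**Conclusion.** The overlap is real but narrow. Opposite instructions occur only at >1.5 to 2.0 x ULN: a hold and an irreversible 16.7% reduction against no change, with loss of alpelisib against no change on recurrence. Above 2.0 x ULN, leaving aside the fractionation exception, both rows hold. They differ in the restart dose when resolved within 14 days, in the restart threshold and in the recurrence rule.

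A reader might infer that any symptom-free rise is handled in opposite ways, or that patients were in fact under- or over-exposed according to site. The documents support neither: the first fails above 2.0 x ULN, and the second would need event or dosing data by site that they do not contain. Nor does the point touch the primary endpoint, the sample size or the test.

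What stands is an unreconciled dose-modification instruction that can blur the recorded reductions, interruptions and discontinuations. The conclusion assumes a rise with no symptoms and no radiologic finding, and the dose figures assume a patient still on 300 mg/day. No view is taken on which action is right.

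**What to change.** The sponsor should reconcile the two Table 6-3 rows so that an isolated enzyme elevation without symptoms or radiologic findings falls under one of them only, reword the other so that it no longer includes that case, and bring Section 6.3.2.1.4 into line. Which action applies is for the sponsor to decide.

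When the dose-modification summaries are interpreted, the report should note that modifications recorded for enzyme elevation may have followed either row.

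The text change is one or two lines and adds no assessments. It is still a protocol amendment, which under Section 12.1 needs approval by the sponsor, the ethics bodies and, where required, health authorities. The reporting note needs no new data and also covers dose decisions already taken.
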